5.5. ADVERSE EVENT AND SERIOUS ADVERSE EVENT REPORTING

- All Serious Adverse Events (SAEs) that occur following the subject's written consent to participate in the study through 100 days of discontinuation of dosing must be reported to BMS Worldwide Safety, whether related or not related to study drug. If applicable, SAEs must be collected that relate to any later protocol-specified procedure (eg, a follow-up skin biopsy).
- Following the subject's written consent to participate in the study, all SAEs, whether related or not related to study drug, are collected, including those thought to be associated with protocol-specified procedures. The investigator should report any SAE occurring after these aforementioned time periods, which is believed to be related to study drug or protocol-specified procedure.
- An SAE report should be completed for any event where doubt exists regarding its seriousness;
- If the investigator believes that an SAE is not related to study drug, but is potentially related to the conditions of the study (such as withdrawal of previous therapy or a complication of a study procedure), the relationship should be specified in the narrative section of the SAE Report Form.
- If the BMS safety address is not included in the protocol document (eg, multicenter studies where events are reported centrally), the procedure for safety reporting must be reviewed/approved by the BMS Protocol Manager. Procedures for such reporting must be reviewed and approved by BMS prior to study activation.
- An appropriate SAE form (e.g. ex-US = CIOMS form or USA = Medwatch form) should be used to report SAEs to BMS. The BMS protocol ID number must be included on whatever form is submitted by the Sponsor/Investigator.
 - The CIOMS form is available at: <http://www.cioms.ch/index.php/cioms-form-i>
 - The MedWatch form is available at: <https://www.fda.gov/downloads/AboutFDA/ReportsManualsForms/Forms/UCM048334.pdf>
-
-
- In accordance with local regulations, BMS will notify investigators of all reported SAEs that are suspected (related to the investigational product) and unexpected (ie, not previously described in the IB). An event meeting these criteria is termed a Suspected, Unexpected Serious Adverse Reaction (SUSAR). Investigator notification of these events will be in the form of a SUSAR Report and provided in the FastTrack portal system.
 - Other important findings which may be reported by BMS as an Expedited Safety Report (ESR) include: increased frequency of a clinically significant expected SAE, an SAE considered associated with study procedures that could modify the conduct of the study, lack of efficacy that poses significant hazard to study subjects, clinically significant safety finding from a nonclinical (eg, animal) study, important safety recommendations from a study data monitoring committee, or Principal Investigator decision to end or temporarily halt a clinical study for safety reasons.
 - Upon receiving an ESR from BMS, the investigator must review and retain the ESR with the IB. Where required by local regulations or when there is a central IRB/IEC for the study, the investigator will submit the ESR to the appropriate IRB/IEC. The investigator and IRB/IEC will determine if the informed consent requires revision. The investigator should also comply with the IRB/IEC procedures for reporting any other safety information.
 - In addition to the Principal Investigator's responsibility to report events to their local HA, suspected serious adverse reactions (whether expected or unexpected) shall be reported by BMS to the relevant competent health authorities in all

concerned countries according to local regulations (either as expedited and/or in aggregate reports).

SAEs, whether related or not related to study drug, and pregnancies must be reported to BMS within 24 hours. SAEs must be recorded on either CIOMS or MedWatch form & pregnancies must be reported on a Pregnancy Surveillance Form or can be submitted on the aforementioned SAE form to BMS.

SAE Email Address: [contact]

SAE [contact]

If only limited information is initially available, follow-up reports are required. (Note: Follow-up SAE reports should include the same investigator term(s) initially reported.)

If an ongoing SAE changes in its intensity or relationship to study drug or if new information becomes available, a follow-up SAE report should be sent within 24 hours to BMS (or designee) using the same procedure used for transmitting the initial SAE report.

All SAEs should be followed to resolution or stabilization.

The Sponsor will reconcile the clinical database SAE cases (case level only) transmitted to BMS Global Pharmacovigilance ([name]). Frequency of reconciliation should be every 3 months and prior to the database lock or final data summary. BMS GPV&E will email, upon request from the Investigator, the GPV&E reconciliation report. Requests for reconciliation should be sent to [contact]. The data elements listed on the GPV&E reconciliation report will be used for case identification purposes. If the Investigator determines a case was not transmitted to BMS GPV&E, the case should be sent immediately to BMS.

5.6. OTHER REPORTING

Non-serious Adverse Event

- Non-serious Adverse Events (AE) are to be provided to BMS in aggregate via interim or final study reports as specified in the agreement or, if a regulatory requirement [eg, IND US trial] as part of an annual reporting requirement.
- Non-serious AE information should also be collected from the start of a placebo lead-in period or other observational period intended to establish a baseline status for the subjects.

A ***non-serious adverse event*** is an AE not classified as serious.

Non-serious Adverse Event Collection and Reporting

The collection of non-serious AE information should begin at initiation of study drug. All non-serious adverse events (not only those deemed to be treatment-related) should be collected continuously during the treatment period and for a minimum of 100 days following the last dose of study treatment.

Non-serious AEs should be followed to resolution or stabilization, or reported as SAEs if they become serious. Follow-up is also required for non-serious AEs that cause interruption or discontinuation of study drug and for those present at the end of study treatment as appropriate.

Laboratory Test Abnormalities

All laboratory test results captured as part of the study should be recorded following institutional procedures. Test results that constitute SAEs should be documented and reported to BMS as such.

The following laboratory abnormalities should be documented and reported appropriately:

- any laboratory test result that is clinically significant or meets the definition of an SAE
- any laboratory abnormality that required the participant to have study drug discontinued or interrupted
- any laboratory abnormality that required the subject to receive specific corrective therapy.

It is expected that wherever possible, the clinical rather than laboratory term would be used by the reporting investigator (eg, anemia versus low hemoglobin value).

Potential Drug Induced Liver Injury (DILI)

Wherever possible, timely confirmation of initial liver-related laboratory abnormalities should occur prior to the reporting of a potential DILI event. All occurrences of potential DILIs, meeting the defined criteria, must be reported as SAEs.

Potential drug induced liver injury is defined as:

- 1) AT (ALT or AST) elevation > 3 times upper limit of normal (ULN)

AND

- 2) Total bilirubin > 2 times ULN, without initial findings of cholestasis (elevated serum alkaline phosphatase)

AND

- 3) No other immediately apparent possible causes of AT elevation and hyperbilirubinemia, including, but not limited to, viral hepatitis, pre-existing chronic or acute liver disease, or the administration of other drug(s) known to be hepatotoxic.

Pregnancy

If, following initiation of the investigational product, it is subsequently discovered that a study participant is pregnant or may have been pregnant at the time of investigational product exposure, including during at least 5 half-lives after product administration, the investigational product will be permanently discontinued in an appropriate manner (eg, dose tapering if necessary for participant).

The investigator must immediately notify [contact] of this event via either the CIOMS, MedWatch or appropriate Pregnancy Surveillance Form in accordance with SAE reporting procedures.

Protocol-required procedures for study discontinuation and follow-up must be performed on the participant.

Follow-up information regarding the course of the pregnancy, including perinatal and neonatal outcome and, where applicable, offspring information must be reported on the CIOMS, MedWatch or appropriate Pregnancy Surveillance Form. A BMS Pregnancy Surveillance Form may be provided upon request.

Any pregnancy that occurs in a female partner of a male study participant should be reported to BMS. Information on this pregnancy will be collected on the Pregnancy Surveillance Form. In order for Principal Investigator or designee to collect any pregnancy surveillance information from the female partner, the female partner must sign an informed consent form for disclosure of this information.

For this reason, female participants in the study will need to use appropriate methods of birth control on study through 5 months post discontinuation of nivolumab. For male participants that have female partners of child bearing potential, they will need to use appropriate methods of birth control on study through 7 months post discontinuation of nivolumab.

Overdose

An overdose is defined as the accidental or intentional administration of any dose of a product that is considered both excessive and medically important. All occurrences of overdose must be reported as an SAE.

Other Safety Considerations

Any significant worsening noted during interim or final physical examinations, electrocardiograms, X-rays, and any other potential safety assessments, whether or not these procedures are required by the protocol, should also be recorded as a non-serious or serious AE, as appropriate, and reported accordingly.

6. BIOMARKER(S) AND CORRELATIVE STUDIES

Baseline PDL1 status will be required for analysis; collection of the diagnostic biopsy specimen upon recurrence or disease persistence will be required for enrollment; a new biopsy will not be mandated upon study entry; collection of diagnostic tissue biopsy at presentation will be required for additional correlative studies; P16 status will be required and performed at local institutions;

6.1. CORRELATIVE TISSUE RESEARCH

Tissue/Specimen Submission

Tumor tissue samples will be collected at pre-treatment and at the time of disease progression if clinically feasible. Tumor tissue collected at the time of pre-treatment may represent frozen samples if collected using a previously established repository or, most likely, formalin-fixed paraffin-embedded (FFPE) blocks. If the former, a section of the tissue will be submitted to the respective lab(s). For the latter, an FFPE tumor block will be submitted to the respective lab(s) (see below for more details). A biopsy at the time of progression is strongly encouraged but if not obtained, does not constitute a protocol violation. If a biopsy is obtained, extra cores may be obtained to allow for biomolecular evaluation. For cases treated at Emory University, tumor tissue samples will be submitted to [name]'s laboratory and will be banked in the department of pathology at Emory University. For cases treated at the Cleveland Clinic, tumor tissue samples will be submitted to [name]'s laboratory and will be banked in his laboratory. The respective labs may exchange samples at will. Genomic profiling of tissue samples will be mainly conducted at the Cleveland Clinic. Note that all tissue obtained for correlative research is supernumerary to the needs of establishing a clinical diagnosis of recurrence.

FFPE tumor samples (Mandatory)

A FFPE tumor block should be submitted with the submission form. A Pathology Report and one H&E stained slide documenting that the submitted block or slides contain tumor should also be submitted with the tissue. The report and H&E stained slide must include the protocol

number and patient's case number. The patient's name and/or other identifying information should be removed from the report. The surgical pathology numbers and information must NOT be removed from the report.

The pre- and post-progression tumor biopsies can be obtained from the primary tumor or lymph node metastasis as a punch biopsy or a core needle biopsy: a punch or core in formalin and secondary 1-2 punches or cores in liquid nitrogen (or dry ice/ethanol slurry). The biopsy samples should be prepared as: 1) formalin-fixed paraffin-embedded tumor blocks and shipped to the designated laboratories in ambient temperature, and 2) flash frozen samples in liquid nitrogen (or dry ice/ethanol slurry) and shipped on dry ice. The frozen specimens can be stored at -80 degree C (-70 degree C to -90 degree C) until ready to ship. If a -80 degree C freezer is not available, samples can be stored short term in a -20 degree C freezer (non-frost-free refrigerator preferred) for up to 7 calendar days (please ship out Monday-Wednesday only).

6.2. CORRELATIVES WITH BLOOD

Blood samples must be submitted with the submission form documenting the date of collection of the sample. Blood samples will be obtained at baseline and prior to each nivolumab infusion during radiation therapy; subsequently blood will be obtained at weeks 18, 30 52, and 104 as outlined in study calendar above. Peripheral blood mononuclear cells (PBMCs) and plasma will be isolated from collected CPTs and cryopreserved as outlined in the blood processing Appendix 3.

Specimen collection summary for correlative studies (Samples can be batched and sent in one shipment)

Specimens for Correlative Studies			
Specimens taken from patient:	Collected when:	Submitted as:	Shipped:
A paraffin-embedded tissue of the primary tumor taken before initiation of treatment	Pre-treatment	Paraffin-embedded tissue block	Block shipped ambient
Fresh frozen tissue of the primary or metastatic tumor taken before initiation of treatment (for research purposes only: OPTIONAL)	Pre-treatment	Frozen tumor in a 2 mL cryovial	Tumor sent frozen on dry ice via overnight carrier
A paraffin-embedded tissue of the primary or metastatic tumor (for research purposes only: OPTIONAL)	At the time of disease progression	Paraffin-embedded tissue block	Block shipped ambient
Fresh frozen tissue of the primary or metastatic tumor (for research purposes only: OPTIONAL)	At the time of disease progression	Frozen tumor in a 2 mL cryovial	Tumor sent frozen on dry ice via overnight carrier
PBMCs and PLASMA: 4 CPTs (8 mL each) of whole blood for	Pre-treatment and prior to each Nivolumab infusion during radiation	Frozen plasma samples containing 2 mL per aliquot in 2 mL cryovials:	Plasma sent frozen on dry ice or liquid nitrogen via overnight carrier

collection of plasma and PBMCs	therapy ; subsequently at wk 18, 30, 52 and 104.	Cryopreserved PBMCs containing 10^7 PBMCs per aliquot in 2 mL cryovials	
--------------------------------	--	---	--

Submit materials for translational research as following:

U. S. Postal Service Mailing Address:

[name] Lab

Department of Microbiology & Immunology

Emory University

[name]

[name]

Or

[name] Laboratory

Cleveland Clinic Foundation

Department of Translational Hematology Oncology Research

[name]

Lerner Res Stockroom

NE6-258 [name] Lab

[name]

For Non-urgent, Non-frozen Specimens Only

Courier Address (FedEx, UPS):

[name] Lab

Department of Microbiology & Immunology

6.3. PROPOSED BIOMARKER EVALUATIONS

A. Despite the unprecedented success of PD-1 targeted therapies a significant number of patients still fail to respond due to mainly unknown reasons. A deeper understanding of the mechanisms underlying responsiveness to blockade of the PD-1 pathway and the identification of predictive biomarkers are thus essential to optimize current treatments and to develop novel treatment approaches in order to improve response rates. Two recent studies analyzing the CD8 T cell response in the peripheral blood of non-small lung cancer and melanoma patients undergoing PD-1 targeted therapies observed an increase in activated and proliferating PD-1+ CD8 T cells in a subset of patients which in combination with tumor burden correlated with clinical outcome (37, 38). We will therefore monitor T cell activation and proliferation in the peripheral blood by multi-parameter flow cytometry of isolated PBMCs including but not limited to the following markers: CD3, CD4, CD8, CD45RA, CCR7, CD27, CD28, CD38, HLA-DR, Ki-67, PD-1. Activated CD38+ HLA-DR+ CD8 T cells at the peak of activation/proliferation will be isolated by flow cytometric sorting followed by DNA and RNA isolation. RNA will be used to transcriptionally profile CD8 T cells responding to therapy using RNAseq. Furthermore, we will use DNA isolated from activated CD8 T cells in the peripheral blood and from frozen tumor tissue to analyze and compare the T cell receptor repertoire of activated/proliferating CD8 T cells in the blood and tumor-infiltrating lymphocytes in the obtained biopsy. It has recently been shown that a particular subset of PD-1+ CD8 T cells expressing the transcription factor TCF-1 possesses stem cell-like feature and is responsible for the proliferative burst of antigen-specific CD8 T cells following PD-1 pathway in a mouse model of persistent viral infection (39). Two recent studies also demonstrated that costimulatory signaling through CD28 is required for CD8 T cell proliferation following PD-1 pathway blockade (40, 41). We hypothesize that increased numbers of CD28+ and/or TCF-1+ among PD-1+ CD8 T cells will be predictive of response to PD-1 pathway blockade. To test this hypothesis, we will characterize tumor-infiltrating lymphocytes by immunofluorescent staining of FFPE sections using antibodies directed against CD4, CD8, PD-1, CD28, TCF-1 as well as additional markers, and correlate with the observed CD8 T cell responses in the blood as well as with clinical outcome.

B. We expect that recurrent cancers will have a substantially higher alteration frequency and a distinct composition of genetic lesions compared to matched treatment naïve tumors. The extent of genetic alterations has been previously associated with response to checkpoint blockade. Therefore, we posit that the extent of non-synonymous mutational load will be predictive of the presence of neo-antigens and therefore predictive of response to nivolumab in patients with recurrent head and neck cancer. We will assess mutational and neoantigen load using whole exome sequencing. We will assess transcriptomic states using RNAseq. We will correlate clinical outcomes with the extent and composition of mutations and identify transcriptomic states (or gene signatures) that could predict improved clinical outcomes (see Appendix 4 for instructions on processing frozen tumor samples for DNA/RNA extraction).

C. Submit materials for translational research as following:

For FFPE tissue samples

Cancer Genetics (CGI)

CGI will provide shipping supplies to each site

7. INVESTIGATIONAL PLAN

7.1. VISIT SCHEDULE

Details of study procedures are in Study Calendar.

7.2 SCREENING PERIOD

Therapeutic Parameters

Pre-study scans used to assess all measurable or non-measurable sites of disease must be done within 30 days prior to registration.

Pre-study CBC (with differential and platelet count) should be done \leq 30 days before registration. All required pre-study chemistries, should be done \leq 30 days before registration.

7.3 END OF STUDY TREATMENT AND FOLLOW-UP PERIOD

Patients will be followed for 2 years from the initiation of treatment. The imaging studies will be performed at baseline and at week 18, 30, 52, and 104. Patients will continue to be followed thereafter by their treating physicians as per standard of care.

7.4 DURATION OF THERAPY

Patients will receive radiation in concurrence with nivolumab and post radiation maintenance nivolumab for 10 cycles unless:

- Radiation is interrupted for > 3 consecutive weeks, in which case they will be removed from the protocol.
- Extraordinary Medical Circumstances: If at any time the constraints of this protocol are detrimental to the patient's health, protocol treatment should be discontinued.
- Patient develops progressive disease; then the patient will discontinue protocol therapy.
- Patient develops unacceptable toxicity; then the patient will discontinue protocol therapy.
- Patients may withdraw consent and withdraw from the study at any time for any reason.

7.5 DURATION OF FOLLOW-UP

For this protocol, all patients, including those who discontinue protocol therapy early, will be followed for response until progression and for survival for 2 years from the start of radiation. All patients must also be followed through completion of all protocol therapy. Patients removed from study for unacceptable adverse events will be followed until resolution or stabilization of the adverse event.

8. STATISTICAL METHODS

Power Caclulation: From the MIRI study, the 1-year PFS rate for class I and II combined was 43.8% (95% CI: 38.6 - 49.7%) Assuming a one sided alpha of 0.05 and an 85% power to detect an improvement in 1-yr PFS from 40% to 55% we estimate 46 patients will need to be accrued in 2.5 years and followed for an additional 2 years (estimated maximum total of 51 patients). Accounting for a 20% drop out rate, 62 patients will need to be consented. The sample size calculation was based on assumptions of exponentially distributed death times and use of the exponential MLE test (42). Definition of clinical outcomes: PFS is defined as months from treatment started to evidenced progression or death and censored at last follow up without progression, and OS is defined as months from treatment started to death or censored at last follow up if alive.

Analysis plan: For primary objective, the 1-yr PFS and its 95% confidence interval will be estimated by Kaplan-Meier method for all patients, as well as in each stratum defined by p16 and RPA status, but this study is not powered at the level of subgroups. For the secondary objectives, Kaplan-Meier method will be used to assess 1-yr OS, PFS, or pattern of failure, and the incidence rate of acute and late toxicities will be described as frequency and percentage. QOL will be summarized by mean and standard deviation. For exploratory objectives, the predictability of related biomarkers (baseline PDL1 status, T-cell activation biomarkers, CD28 and TCF1 positivity on T lymphocytes and other biomarkers) to clinical

outcomes (OS and PFS) will be explored using both univariate and multivariable Cox proportional hazards model controlling for potential confounders.

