Objectives	
Primary Objectives:
 
1- To assess the 1-year PFS for patients with RPA class I and II disease treated with nivolumab and IMRT re-irradiation
 
Secondary Objectives:
 
1- Evaluate the OS of patients treated with re-irradiation and nivolumab 2- Evaluate patient QOL 3- Evaluate patterns of failure including rates of locoregional failure and distant failure 4- Identify and estimate the incidence rate of acute and late toxicities associated with combined re-irradiation and nivolumab followed by nivolumab
 
Exploratory Objectives:
 
 • To identify potential biomarkers related to clinical benefit to concurrent nivolumab and re-irradiation in patients with recurrent HNSCC.

SAEStudy Design	
This will be a phase II single arm study of IMRT re-irradiation in combination with nivolumab in the concurrent and maintenance setting. Patients with RPA class I and II based on the recursive partitioning analysis (RPA) classes reported by Ward et al (ASTRO 2016) will be enrolled. The allowable treatment approaches include IMRT. Based on this analysis, only patients with RPA classes I and II will be included; Class III patients will be excluded.
 
RT will be given as 60-66Gy in once daily fractions (2 Gy per fraction).
 
Nivolumab will be administered 2 weeks prior to the beginning of radiation therapy (1 dose at Week -2) and continue every 2 weeks during radiation (4 doses at Weeks 0, 2, 4, 6) for a total of 5 doses. Nivolumab will then be given every 4 weeks for 10 additional doses for a total of 15 doses of Nivolumab.

Number of Patients	
From the MIRI study, the 1-year PFS rate for class I and II combined was 43.8% (95% CI: 38.6 - 49.7%). Assuming a one sided alpha of 0.05 and an 85% power to detect an improvement in 1-yr PFS from 40% to 55% we estimate 46 patients will need to be accrued in 2.5 years and followed for an additional 2 years (estimated maximum total of 51 patients). Accounting for a 20% drop out rate, 62 patients will need to be consented.

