3. STUDY POPULATION

Number of Centers

Three sites will be involved.

Number of Participants

A total of 46 patients will need to be accrued in 2.5 years and followed for an additional 2 years (estimated maximum total of 51 patients). Accounting for a 20% drop out rate, 62 patients will need to be consented.

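### The 85% power at 46 patients fits 2 to 4.5 years of follow-up per patient; if PFS follow-up stops at 2 years, as Section 7.3 suggests, the sizing test has about 81-82% at 46 and about 85% at 50-51

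*Combined protocol and SAP*

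**What the plan says.** Section 8 gives the sample size as "46 patients will need to be accrued in 2.5 years and followed for an additional 2 years", with an "estimated maximum total of 51 patients". The target is 85% power at one-sided alpha 0.05 for a rise in 1-year PFS from 40% to 55%. The synopsis makes the same statement, and Section 3 repeats the patient numbers and times. On method, Section 8 states: "The sample size calculation was based on assumptions of exponentially distributed death times and use of the exponential MLE test". After 20% drop-out, 62 patients are to be consented.

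Section 7.3 describes follow-up per patient: "Patients will be followed for 2 years from the initiation of treatment". The last scheduled imaging there and in the study calendar is week 104, after which care passes to the treating physicians. Sections 7.5 and 3.1.4 follow response up to progression and survival for 2 years from the start of radiation. Calendar footnote h allows further scans when progression is suspected.

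Section 8 counts progression or death as a PFS event and otherwise has PFS "censored at last follow up without progression", with no week-104 limit. The primary analysis is that "the 1-yr PFS and its 95% confidence interval will be estimated by Kaplan-Meier method for all patients".

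**The concern.** The power statement and the follow-up sections describe different observation periods. Accrual over 2.5 years plus 2 more years keeps the earliest patients under observation for up to 4.5 years, whereas Section 7.3 stops at 2 years for everyone. An exponential MLE test gains information from every event whenever it occurs, so ending follow-up at 2 years removes events that the sizing counted on.

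Two things are at stake. One is whether the stated 85% matches the follow-up that will actually be collected. The other is practical: without an instruction, sites may stop recording progression and death at week 104 for early enrollees. Because PFS includes death, the 2-year limit on survival follow-up in Sections 7.5 and 3.1.4 matters even if progression is followed for longer.

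**Working it through.** **Inputs.** From Section 8: one-sided alpha 0.05, 1-year PFS 0.40 versus 0.55, accrual 2.5 years, further follow-up 2 years, n = 46 (maximum 51). From Section 7.3: 2 years per patient. Assumed, because the documents do not say: uniform accrual, no loss to follow-up, and the scale on which the MLE is tested.

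**Hazards per year.** λ0 = −ln 0.40 = 0.916 and λ1 = −ln 0.55 = 0.598.

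**Probability of an observed event.**
- Follow-up of 2 to 4.5 years: d(λ) = 1 − (e^(−2λ) − e^(−4.5λ))/(2.5λ). This gives d(λ0) = 0.937 and d(λ1) = 0.843.
- Capped at 2 years: d(λ) = 1 − e^(−2λ). This gives d(λ0) = 1 − 0.40² = 0.840 and d(λ1) = 1 − 0.55² = 0.6975.

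**Expected events under 55%.** At 46: 46 × 0.843 = 38.8, against 46 × 0.6975 = 32.1 if capped. At 51: 43.0 against 35.6.

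**Reproducing the plan's 46.** On the cube-root scale the standard error is λ^(1/3)/(3√(n·d(λ))), taken under the null for the critical value (s0) and under the alternative for power (s1). The difference in cube roots is 0.9713 − 0.8424 = 0.1289. At n = 46 with 2 to 4.5 years, s0 = 0.0493 and s1 = 0.0451, so power = Φ((0.1289 − 1.645 × 0.0493)/0.0451) = Φ(1.06) = 85.5%. At n = 45 it is 84.8%, so 46 is the first size to reach 85%.

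**Same test with a 2-year cap.** At n = 46, s0 = 0.0521 and s1 = 0.0496, so power = Φ((0.1289 − 1.645 × 0.0521)/0.0496) = Φ(0.87) = 80.8%.

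| n | cube-root, 2 to 4.5 years | cube-root, capped | simulation at exact 5%, capped |
|---|---|---|---|
| 46 | 85.5% | 80.8% | about 82% |
| 50 | 88.1% | 83.7% | about 85% |
| 51 | 88.7% | 84.3% | about 85% |

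The simulation sets the critical value so that the test has exactly 5% size. Uncapped, it gives 86.9% at 46 and 89.5% at 51. The row for 50 is the number left after drop-out: 62 × 0.8 = 49.6.

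**Sensitivity to the form of the test.** Across log-hazard, hazard, mean and cube-root scales with different variance choices, capped power runs from about 76% to 84% at 46 and from about 80% to 87% at 51. Counting the cap from the start of radiation, two weeks after the first dose (2.04 years), gives 81.1% and 84.6% in the cube-root form.

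**The planned analysis.** For a normal-approximation test of the 1-year Kaplan-Meier rate against 40%, with no censoring before 1 year, power is Φ((0.15 − 1.645√(0.24/n))/√(0.2475/n)): 66% at 46 and 70% at 51. It reaches 85% at n = 78. No follow-up after year 1 enters this, so the cap does not change it.

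**The case against.** The strongest reply is that no arithmetic error has been shown. The 46 reproduces under the design as Section 8 states it, and the documents do not clearly cap PFS. Sections 7.5 and 3.1.4 follow response until progression, footnote h permits later scans, and the censoring rule has no week-104 limit. That stands: the finding is conditional, and a reader who concludes that the 85% is simply wrong goes further than the text allows.

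A reader might also infer that a cap leaves the trial short of 85% even at 51, since the cube-root approximation gives 84% there and needs 53 patients for 85%. This does not hold up. The various scales are monotone transformations of one estimate, events divided by person-time. Once the critical value is set to exactly 5% they are the same test, and that test has about 85% power at 50 and at 51. The spread between forms is mostly error in the normal approximation.

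Nor does an exact 46 prove which follow-up was assumed. The log-hazard form with null variance needs 47 under a 2-year cap, so a capped calculation cannot be ruled out. The match with the stated 2.5 plus 2 years favours the longer follow-up.

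Finally, the exponential MLE test does not appear in the analysis plan, so the cap refines the power of a test that the plan does not say will be run. That is true, and it is why the point is minor. The 66% and 70% figures are a separate matter of what the 85% refers to; they are not a consequence of the cap.

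**Conclusion.** The concern holds as a conditional and minor point. Section 8 and Section 7.3 imply different follow-up, and the text does not settle which governs PFS. If PFS follow-up is capped at 2 years, power of the sizing test at 46 is about 81-82% rather than 85%, a shortfall of 3-4 points, and there is essentially none at 50-51. If it is not capped, the stated 85% at 46 stands.

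The documents do not support reading this as a threat to the primary result: the 1-year Kaplan-Meier estimate and its interval are the same under either rule. Under neither rule does the 85% describe that analysis. The figures rest on exponential PFS, uniform accrual, no loss to follow-up and an unstated form of the MLE test. Confidence is medium, mainly because of the last of these and the ambiguity about the cap.

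**What to change.** Reconcile Sections 7.3, 7.5 and 3.1.4 with Section 8 by stating whether PFS follow-up ends 2 years after each patient starts.

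- If it does, restate power in Section 8 and the synopsis as about 81-82% at 46 and about 85% at 50-51, and name the form of the test. This costs wording only.
- If it does not, state that progression and death dates, including those from standard-of-care follow-up, are recorded until 2 years after the last patient starts treatment. This costs chart-based collection of dates for earlier enrollees and adds no study procedures.

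In either case, add a sentence saying that the power figure belongs to the exponential MLE test and not to the planned 1-year Kaplan-Meier analysis, and give the corresponding figures for a normal-approximation test of the 1-year rate against 40% (about 66% at 46 and 70% at 51).
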